#### 11.2.5 Clinical Benefit rate

Clinical benefit rate: defined as CR, PR and stable disease (SD)  $\geq$  24 weeks.

### 11.3 Antitumor Effect – Hematologic Tumors

N/A

### 11.4 Other Response Parameters

#### 11.4.1 Definition of Tumor Response Using Immune-Related Response Criteria (irRC)

The sum of the longest diameter of lesions (SPD) at tumor assessment using the immune-related response criteria (irRC) for progressive disease incorporate the contribution of new measurable lesions. Each net Percentage Change in Tumor Burden per assessment using irRC criteria accounts for the size and growth kinetics of both old and new lesions as they appear.

##### 11.4.1.1 Impact of New Lesions on irRC

New lesions in and of themselves do not qualify as progressive disease. However, their contribution to total tumor burden is included in the SPD which in turn feeds into the

irRC criteria for tumor response. Therefore, new non-measurable lesions will not discontinue any subject from the study.

#### 11.4.1.2 Definition of Target Lesions Response Using irRC

- **irComplete Response (irCR):** Complete disappearance of all target lesions. This category encompasses exactly the same subjects as “CR” by the mWHO criteria.
- **irPartial Response (irPR):** Decrease, relative to baseline, of 50% or greater in the sum of the products of the two largest perpendicular diameters of all target and all new measurable target lesions (i.e., Percentage Change in Tumor Burden). Note: the appearance of new measurable lesions is factored into the overall tumor burden, but does not automatically qualify as progressive disease until the SBD increases by  $\geq 25\%$  when compared to SPD at nadir.
- **irStable Disease (irSD):** Does not meet criteria for irRC or irPR, in the absence of progressive disease.
- **irProgressive Disease (irPD):** At least 25% increase Percentage Change in Tumor Burden (i.e. taking SPD of all target lesions and any new lesions) when compared to SPD at nadir.

#### 11.4.1.3 Definition of Non-Target Lesions Response Using irRC

- **irComplete Response (irCR):** Complete disappearance of all non-target lesions. This category encompasses exactly the same subjects as “CR” by the mWHO criteria.
- **irPartial Response (irPR) or irStable Disease (irSD):** Non-target lesion(s) are not considered in the definition of PR; these terms do not apply.
- **irProgressive Disease (irPD):** Increases in number or size of non-target lesion(s) does not constitute progressive disease unless/until the Percentage Change in Tumor Burden increases by 25% (i.e. the SPD at nadir of the target lesions increases by the required amount).

#### 11.4.1.4 Definition of Overall Response Using irRC

Overall response using irRC will be based on these criteria:

- **Immune-Related Complete Response (irCR):** Complete disappearance of all tumor lesions (target and non-target) together with no new measurable/unmeasurable lesions for at least 4 weeks from the date of documentation of complete response.
- **Immune-Related Partial Response (irPR):** The sum of the products of the two largest perpendicular diameters of all target lesions is measured and captured as the SPD baseline. At each subsequent tumor assessment, the SPD of the two largest perpendicular diameters of all target lesions and of new measurable lesions are added together to provide the Immune Response Sum of Product Diameters (irSPD). A decrease, relative to baseline, of the irSPD compared to the previously SPD baseline of 50% or greater is considered an irPR.
- **Immune-Related Stable Disease (irSD):** irSD is defined as the failure to meet criteria

for immune complete response or immune partial response, in the absence of progressive disease

- **Immune-Related Progressive Disease (irPD):** It is recommended in difficult cases to confirm PD by serial imaging. Any of the following will constitute PD:
  - At least 25% increase in the SPD of all target lesions over baseline SPD calculated for the target lesions.
  - At least 25% increase in the SPD of all target lesions and new measurable lesions (irSPD) over the baseline SPD calculated for the target lesions.

Criteria for determining overall response by irRC are summarized as follows:

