**Immune-Related Response Criteria Definitions**

Target Lesion Definition	Non-Target Lesion Definition	New Measurable Lesions	New Unmeasurable Lesions	Percent change in tumor burden (including measurable new lesions when present)	Overall irRC Response
Complete Response	Complete Response	No	No	-100%	irCR
Partial Response	Any	Any	Any	≥ -50%	irPR
				<-50% to <+25%	irSD
				>+25%	irPD
Stable Disease	Any	Any	Any	<-50% to <+25%	irSD
				>+25%	irPD
Progressive Disease	Any	Any	Any	≥+25%	irPD

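### irRC progression is measured from nadir SPD in 11.4.1.2 and 11.4.1.3 but from baseline SPD in 11.4.1.4, giving two thresholds once SPD has fallen below baseline

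*Combined protocol and SAP*

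**What the plan says.** Section 11.4.1.2 (target lesions) defines irPD as a rise of at least 25% in tumor burden: "i.e. taking SPD of all target lesions and any new lesions) when compared to SPD at nadir". The note to its irPR definition uses the nadir reference again and says that "the appearance of new measurable lesions is factored into the overall tumor burden". Section 11.4.1.3 (non-target lesions) allows irPD only once tumor burden has risen by 25%, which it explains as "the SPD at nadir of the target lesions increases by the required amount".

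Section 11.4.1.4 opens with "Overall response using irRC will be based on these criteria". Either of its two irPD bullets is enough for progression. The first is "At least 25% increase in the SPD of all target lesions over baseline SPD calculated for the target lesions". The second applies the same 25% to "target lesions and new measurable lesions (irSPD) over the baseline SPD calculated for the target lesions". For irPR, the same section says "A decrease, relative to baseline, of the irSPD compared to the previously SPD baseline of 50% or greater is considered an irPR".

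The summary table that follows has a single column, "Percent change in tumor burden (including measurable new lesions when present"), and does not name the reference for the change. Its first column is the target-lesion category.

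irRC progression is used in two places. Section 5.5 lists progression by iRANO and/or irRC among the criteria for ending protocol therapy. Section 13.7 lists a single-compartment irRC PFS among four PFS definitions to be compared.

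**The concern.** A 25% rise from nadir and a 25% rise from baseline are different events in any patient whose SPD has fallen. The patients concerned are those whose disease shrank and then regrew, for whom the decision to treat beyond first worsening matters most. Two investigators following different subsections could continue one such patient and stop another at the same tumor burden. An irRC PFS with two possible event definitions also weakens the comparison of criteria planned in 13.7, and leaves a choice that could be made after the data are seen.

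**Working it through.** The plan states no figure to reproduce. The check compares the two rules directly and then asks what would follow.

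**1. Thresholds.** Set baseline SPD to 100 and let N be the nadir.
- Nadir rule (11.4.1.2, 11.4.1.3): irPD at 1.25 × N.
- Baseline rule (11.4.1.4): irPD at 1.25 × 100 = 125.
- Regrowth from nadir needed under the baseline rule: 125/N − 1.

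| Nadir N | Nadir rule | Baseline rule | Regrowth from nadir, nadir rule | Regrowth from nadir, baseline rule |
|---|---|---|---|---|
| 100 | 125 | 125 | 25% | 25% |
| 90 | 112.5 | 125 | 25% | 39% |
| 70 | 87.5 | 125 | 25% | 79% |
| 50 | 62.5 | 125 | 25% | 150% |
| 30 | 37.5 | 125 | 25% | 317% |

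**2. Whether the sections describe different quantities.** They do not. The sum in 11.4.1.2 already includes new lesions, so it is in substance the irSPD of 11.4.1.4.

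**3. Whether the table settles it.** Take N = 50 with regrowth to 62.5. Section 11.4.1.2 makes this target-lesion PD. Read from baseline, the change is 62.5 − 100 = −37.5%, and the target-PD row lists only +25% or more, so no row applies. Reading the whole column from nadir fills that row, but it also moves the −50% irPR limit to nadir, which contradicts 11.4.1.2 and 11.4.1.4. Reading everything from baseline contradicts the irPD rule in 11.4.1.2.

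**4. Overlap if nadir is adopted.** irPR is measured from baseline and needs SPD at or below 50. Under the nadir rule, irPD and irPR can both be met when 1.25 × N ≤ 50, that is N ≤ 40. At N = 30, any SPD from 37.5 to 50 meets both.

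**5. Effect on the dated event (illustration).** Assume a nadir at week 6, exponential regrowth SPD(t) = N × 2^((t − 6)/DT) with doubling time DT in weeks, and later scans exactly at weeks 12, 18, 24, 33 and 42. The scan intervals follow section 11. The ±1 week window is ignored, and the doubling times are not in the documents.

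| Rule and nadir | DT 4 | DT 8 | DT 12 | DT 16 | DT 24 |
|---|---|---|---|---|---|
| Nadir rule, any N: irPD week | 12 | 12 | 12 | 12 | 18 |
| Baseline rule, N = 90: irPD week | 12 | 12 | 12 | 18 | 18 |
| Baseline rule, N = 70: irPD week | 12 | 18 | 18 | 24 | 33 |
| Baseline rule, N = 50: irPD week | 12 | 18 | 24 | 33 | 42 |
| Delay, N = 90 (weeks) | 0 | 0 | 0 | 6 | 0 |
| Delay, N = 70 (weeks) | 0 | 6 | 6 | 12 | 15 |
| Delay, N = 50 (weeks) | 0 | 6 | 12 | 21 | 24 |

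**6. Patients with a deep nadir (illustration).** Treat a RECIST PR as roughly a halving of SPD (0.7² = 0.49). The null and alternative response rates in 13.6.1 then give 0.10 × 45 = 4.5 to 0.25 × 45 = 11.25 patients with a nadir at or below about 50. Patients with smaller falls are additional and cannot be counted.

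**The case against.** The strongest reply is that a usable rule exists. Stopping therapy and dating PFS both need an overall call, 11.4.1.4 is headed as the overall definition, and the two preceding subsections are components. That is a natural reading and gives baseline a textual basis. It does not reconcile the sections, because the component rule covers the same sum and the table takes the target-lesion category as an input to overall response. The table gap in step 3 does depend on mixing references. It shows the same conflict and is not a second defect.

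The consequence is also narrow, and this stands. irRC PFS has no hypothesis or power attached, and the objectives in 1.4 name irRC only for response rate. Section 5.5 permits rather than requires continuation, and provides other exits, including iRANO progression, adverse events, withdrawal and investigator judgment. Section 11.4.1.4 also recommends serial imaging in difficult cases.

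The size is largely assumed, and this stands too. The 4.5 to 11.25 patients are those with a deep nadir, not those whose irPD date would change, and the rates used are extracranial. The scan window can remove a delay: with N = 70 and DT = 8 the baseline threshold is crossed at about week 12.7, so a permitted week-13 scan removes the 6-week difference.

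Finally, baseline throughout would be simpler, since irPR and irPD could then not coincide. That is a fair argument about which rule to choose. It is not an argument for leaving both in place.

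**Conclusion.** The concern holds. The protocol states two incompatible irPD rules for the same quantity, and neither is given precedence. Where SPD has fallen below baseline, the thresholds differ by the factor 100/N: 1.11 at a nadir of 90 and 2 at a nadir of 50. Patients who never shrink are unaffected, and even where SPD fell, the scan at which irPD is dated may be the same. The 0 to 24 week range rests on the assumed week-6 nadir, exponential regrowth, doubling times and exact scan dates. The number of patients affected cannot be derived from the documents.

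The reach is the irRC stopping criterion in 5.5 and the exploratory irRC PFS in 13.7. irPR is measured from baseline in both texts, so irRC response is not directly affected. The inconsistency should be corrected because it bears on treatment decisions as well as on an exploratory analysis.

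**What to change.** Use one reference throughout. The preferred change is:
- Rewrite both irPD bullets in 11.4.1.4 as a rise of 25% or more in SPD/irSPD over nadir, with baseline as the reference if it is the smallest value. This matches 11.4.1.2, 11.4.1.3 and the RECIST rule in 11.2.3.1.
- State that irPD overrides irPR and irSD when both are met at one assessment, and whether such a scan can confirm an earlier irPR under 11.4.1.5.
- Label the table so that irPR is read from baseline and irPD from nadir, with ≥ +25% in every irPD row.
- Apply the same rule to 5.5 and to irRC PFS.

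The alternative is to keep baseline and edit 11.4.1.2 and 11.4.1.3. This also removes the conflict and needs no rule for irPD and irPR coinciding.

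The cost is protocol wording, with no new measurements or required analyses. The nadir rule does have a clinical downside: some responders reach irPD earlier than under the baseline rule. A sensitivity analysis using the baseline reference is optional.

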#### 5.5 Criteria for Taking a Participant Off Protocol Therapy

Duration of therapy will depend on individual response, evidence of disease progression and tolerance. In the absence of treatment delays due to adverse event(s), treatment may continue for an indefinite number of cycles, or until one of the following criteria applies:

- Disease progression by iRANO and/or irRC criteria.
  - Please note that although the primary endpoint is bi-compartmental PFS as

defined by standard RANO-BM (for CNS) and RECIST 1.1 (for non-CNS), patients may remain on protocol therapy until the time of disease progression by iRANO and/or irRC criteria. The immune criteria allow treatment beyond initial radiographic worsening of disease in order to distinguish between pseudoprogression and true disease progression.

- Intercurrent illness that prevents further administration of treatment
- Unacceptable adverse event(s)
- Participant demonstrates an inability or unwillingness to comply with the medication regimen and/or documentation requirements
- Participant decides to withdraw from the protocol therapy
- General or specific changes in the participant's condition render the participant unacceptable for further treatment in the judgment of the treating investigator

Participants will be removed from the protocol therapy when any of these criteria apply. The reason for removal from protocol therapy, and the date the participant was removed, must be documented in the case report form (CRF) and in the CTMS system (OnCore). Alternative care options will be discussed with the participant.

In the event of unusual or life-threatening complications, treating investigators must immediately notify the Overall PI, [name] at [REDACTED]

Participants with a documented complete response (CR) may elect to stop Atezolizumab. Subjects who stop atezolizumab with a CR may be eligible for additional atezolizumab therapy if they progress after stopping study treatment. This retreatment is termed the Second Course Phase of this study and is only available if the study remains open and the subject meets the following conditions:

- Stopped initial treatment with atezolizumab after attaining a confirmed and documented CR according to RECIST 1.1, was treated for at least 24 weeks with atezolizumab before discontinuing therapy, and received at least two treatments with atezolizumab beyond the date when the initial CR was declared.

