## 11. MEASUREMENT OF EFFECT

In this study, response and progression in the CNS and in non-CNS sites will be evaluated and recorded separately in this trial. For the purposes of this study, participants should be re-evaluated for response every 6 weeks for the first 24 weeks and then every 9 weeks thereafter. For participants who achieve a sustainable response after 1 year on protocol therapy, re-evaluation can be performed every 12 weeks.

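### Progression under irRC is measured from nadir in Sections 11.4.1.2 and 11.4.1.3 but from baseline in Section 11.4.1.4, and nothing states which governs

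*Combined protocol and SAP*

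**What the plan says.** Section 11.4.1.2 defines target-lesion irPD as a rise of at least 25% in "Percentage Change in Tumor Burden (i.e. taking SPD of all target lesions and any new lesions) when compared to SPD at nadir". The note under irPR in the same section repeats the nadir reference. Section 11.4.1.3 lets non-target growth count only once tumor burden has risen by 25%, which it explains as the point where "the SPD at nadir of the target lesions increases by the required amount".

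Section 11.4.1.4, on overall response, gives two irPD bullets, either of which is sufficient. The first is "At least 25% increase in the SPD of all target lesions over baseline SPD calculated for the target lesions". The second applies the same 25% to target lesions "and new measurable lesions (irSPD) over the baseline SPD calculated for the target lesions".

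The table of irRC definitions that follows takes the target-lesion category as its first input. It lists +25% as the irPD cut-off for percent change in tumor burden and does not say whether the change is from baseline or from nadir.

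Section 5.5 lists "Disease progression by iRANO and/or irRC criteria" among the reasons to stop, and adds: "Participants will be removed from the protocol therapy when any of these criteria apply". Section 13.7 lists PFS by irRC among the exploratory comparisons.

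**The concern.** Section 11.4.1.2 and the second bullet of Section 11.4.1.4 describe essentially the same quantity, target plus new lesions, and compare it with different references. The two agree only when SPD never fell below baseline. For a patient who shrank and then regrew, two readers who each follow the text can record irPD on different scans.

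Two things depend on that date: when atezolizumab stops for a patient kept on drug until irRC progression, and the event date in the exploratory irRC PFS. The patients concerned are those who had some benefit, for whom treatment duration and irRC PFS are of most interest.

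**Working it through.** The plan states no figure to reproduce. The check compares the definitions and then sizes the gap.

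**Thresholds.** Set baseline SPD to 100 and let n be nadir SPD divided by baseline SPD. The nadir rule triggers at 1.25 × 100n = 125n. The baseline rule triggers at 1.25 × 100 = 125. Their ratio is 1/n. The shrinkage values below are illustrative.

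| Fall in SPD | n | Nadir rule | Baseline rule | Rise from nadir needed under the baseline rule |
|---|---|---|---|---|
| 0% | 1.00 | 125 | 125 | +25% |
| 20% | 0.80 | 100 | 125 | +56% |
| 50% | 0.50 | 62.5 | 125 | +150% |
| 60% | 0.40 | 50 | 125 | +212.5% |
| 75% | 0.25 | 31.25 | 125 | +400% |

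**One patient, two answers.** Take SPD 100, then 40, then 55.
- Section 11.4.1.2: 55/40 − 1 = +37.5%, so irPD.
- Section 11.4.1.4: 55/100 − 1 = −45%. This is neither a 25% rise nor a 50% fall, so irSD.

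**Does the table settle it?** Under Section 11.4.1.2 this patient's target category is progressive disease. The only entry in that row of the table is a change of +25% or more. Measured from baseline the change is −45%, so no cell fits. Measured from nadir the result is irPD, which contradicts Section 11.4.1.4. The table does not reconcile the two.

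**Scan schedule.** Section 11 says "participants should be re-evaluated for response every 6 weeks for the first 24 weeks and then every 9 weeks thereafter", with 12-weekly scans allowed for sustained responders after one year. One scan can cross both thresholds, and the dates then agree. For that, SPD must rise by a factor of more than 1/n between consecutive scans: more than double after a 50% fall, more than 1.25-fold after a 20% fall.

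**Position relative to RECIST 1.1.** Assume all diameters change in proportion. A 25% rise in SPD is √1.25 − 1 = +11.8% in diameter. RECIST progression at +20% in diameter is 1.20² = 1.44 in SPD, that is 144n (leaving aside its 5 mm minimum). After a 50% fall the order is 62.5 (irPD from nadir), 72 (RECIST), 125 (irPD from baseline). After a 20% fall it is 100, 115.2, 125.

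**Number of patients.** Section 13.6.1 plans on extracranial RECIST response rates of 10% (null) and 25% (alternative). With 45 patients, 45 × 0.10 = 4.5 and 45 × 0.25 = 11.25, so about 5 to 11 expected responders. Only those who regrow while on drug face the conflict in their stopping date.

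**Overlap of irPR and irPD.** Under the nadir rule one scan can meet both when 125n ≤ 50, that is n ≤ 0.40.

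**The case against.** The best counter-argument is that Section 11.4.1.4 governs. It is the section headed overall response, while 11.4.1.2 and 11.4.1.3 are lesion-level, and a stopping decision or PFS event is naturally an overall response. The table also runs its cut-offs down one percent-change column; the −50% for irPR is against baseline, so +25% may be as well. This makes a baseline reading arguable. It does not settle the matter, because no text gives 11.4.1.4 precedence and the table draws on the target-lesion category that 11.4.1.2 defines from nadir.

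A second argument also favors baseline. Section 5.5 says the immune criteria exist to allow treatment past initial radiographic worsening. Under the nadir rule a regrowing responder meets irPD before RECIST progression, which runs against that purpose. This stands as a reason for the sponsor to choose deliberately. It is not decisive, because without prior shrinkage irPD (125) precedes RECIST progression (144) under either reference.

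Third, Section 1.1 describes atezolizumab until RANO-BM or RECIST progression, and Section 5.5 says only that patients may continue to irRC progression. If a patient stops at RECIST progression, the difference in stopping point after a 50% fall is 62.5 against 72, not 62.5 against 125. This stands: the full gap applies only to patients kept on drug to irRC progression.

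**Conclusion.** The inconsistency is real and should be removed; its severity is minor to moderate. The triggers differ by a factor of 1/n: twofold after a 50% fall in SPD, 1.25-fold after a 20% fall, and not at all without shrinkage. It can move the irRC off-therapy date and the exploratory irRC PFS date in patients who shrank and then regrew.

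Three stronger readings are not supported.
- A reader might infer that the main results are at risk. Primary PFS uses RANO-BM and RECIST 1.1 (Section 13.5). Extracranial response rate, OS and the power do not use irRC. The irRC response rate rests on irPR, which is against baseline in both Sections 11.4.1.2 and 11.4.1.4.
- A reader might take 5 to 11 of 45 as a ceiling. It is the expected number of responders at two planning rates. The true rate may lie outside them, smaller shrinkage also opens a gap, and many responders may never regrow on drug.
- A reader might express the gap as a number of weeks or cycles. The documents give no regrowth rate, so any such figure would rest on an assumed doubling time as well as on the scan interval.

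Nor do the documents prove which reference was intended. They show only that one must be chosen.

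**What to change.** Use a single irPD reference throughout Section 11.4.1. The smallest SPD or irSPD recorded on study, baseline included, is the natural choice: Sections 11.4.1.2 and 11.4.1.3 already use nadir, and RANO-BM (Section 11.1.1.4) and RECIST 1.1 (Section 11.2.3.1) use the smallest sum on study. Reword both irPD bullets in Section 11.4.1.4 accordingly. In the table, state that irPR is measured against baseline and irPD against nadir, with irPD taking precedence when one scan meets both.

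The edit is a few words and leaves the sample size, the definition of the primary analysis and the scan schedule as they are. It has a clinical cost: responders who regrow stop atezolizumab earlier than under Section 11.4.1.4. With proportional growth they stop before RECIST progression, at about +12% rather than +20% in diameter. Body imaging should therefore continue to RECIST progression under the existing 6-to-12-week follow-up (Section 10, note h). Missed scans off therapy are not violations there, so some RECIST dates could go unobserved.

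If the sponsor intended baseline, leave Section 11.4.1.4 as it is, change Sections 11.4.1.2 and 11.4.1.3, and name baseline in the table.
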